3. RATIONALE

To enhance the care of patients with a telepsychiatric consult, Atrium Health has designed a Behavioral Health Virtual Patient Navigation (BH-VPN) program. Navigators will monitor patients and assist with navigation through a weekly phone call after their index ED encounter for up to 45 days post ED discharge. The BH-VPN aims to improve patient outcomes through standardized approaches that leverage analytics and technology, while bridging care coordination. When a patient presents to a participating Atrium Health ED, those with a telepsychiatric consult completed on a randomized intervention day, during the hours of operation, are provided the option of participating in the BH-VPN program. A patient can choose not to receive care by a navigator post discharge.

The BH-VPN program includes the following key components: introduction to the patient follow-up process prior to ED discharge, follow-up evaluation within 72 hours by phone and weekly contact, confirmation that a follow-up visit is scheduled, where applicable confirm in-network follow-up appointments are completed with an Atrium Health provider, and placement into an appropriate case management program, if needed. There may be cases where patients are eligible to enroll in full case management programs based on their insurance and other criteria. For example, if a patient has Medicaid through Cardinal Innovations, a managed care organization providing local behavioral health care, and meets specific criteria, would no longer require navigation services. A patient's contact with the BH-VPN program ends after 45 days following ED discharge, or if there is a failure to contact, becomes enrolled with a case-management program, declines services, or the patient dies. For those patients enrolled in a case management program, then navigator will ensure the patient is in contact with case management program staff before ending contact with the patient.

This research project is a pragmatic, randomized evaluation of a quality improvement initiative which seeks to evaluate the effects of standardizing the use of a BH-VPN program among patients with a telepsychiatric consult. The outcomes evaluation of this intervention has been designed to integrate with routine care and minimize frontline staff burden by deploying an evaluation in a real-world setting.

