5. OVERALL DESIGN

5.1. Outcome Variables

5.1.1. Primary Outcome Variable

The primary outcome variable is ED to hospital admission. This is a patient that presents to an Atrium Health ED and then is admitted for any reason. A patient's disposition is tracked in the electronic medical record. The disposition is simply indicated as admitted or not admitted.

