5.3. Behavioral Health Virtual Patient Navigation (BH-VPN) Program

The BH-VPN outlines the flow of patients from initial contact to their follow-up calls (see Appendix 1). In the existing ED workflow, patients are identified by a clinician in the ED as needing psychiatric evaluation and a referral is made to a tele-psych provider for a virtual consult. Patients who complete a telepsychiatric consult in the ED can be enrolled to either the control or intervention arm based on a randomization scheme that randomly allocates days that navigators are available. Psychiatrists are reminded through daily communication as to whether the BH-VPN program is available and the ED locations. The psychiatrist will make a recommendation to admit or discharge the patient. The ED physician will make the final decision on whether to admit or discharge the patient from the ED. Patients that have a discharge recommendation on days the program is available, will be offered the BH-VPN program. Enrolled patients are followed for up to 45 days.

If a discharge recommendation is made, a patient will be approached again by the navigator virtually for enrollment into the BH-VPN program. The patient has the option not to be followed by the navigator. Before discharge, the navigator will complete an initial virtual behavioral health assessment. The initial health assessment contains information such as preferred communication method, primary care provider, psychiatry provider, PHQ-9 screening, collateral resources, recent ED and hospital utilization, substance use disorder, medication barriers, appointment barriers, community resources, and crisis planning.

The follow-up assessments, which will occur during navigation phone calls at least weekly, may include information such as a suicide ideation safety screening, an appointment reminder, appointment barrier evaluations, medication obtainment follow-up, substance use disorder follow-up, PHQ-9 screening, supportive listening, psychoeducation, community resource follow-up, and additional crisis planning. Phone calls are weekly as standard care but may be more often depending on the individual needs of the patient. Appointments are dependent on a patient's specific needs and may be with a therapist or psychiatrist as well as other providers in the community such as primary care or referral to a community provider.

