5.5. Patient Graduation from the BH-VPN Program

For the intervention arm, successful completion is defined as

- Enrolled for 45 days post ED admit date
- Enrolled in another Care Management program

For the intervention arm, failure to complete is defined as

- Unable to connect: 4 calls attempted over 12 days
- Death
- Declined services initially or after enrollment

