6.2. Statistical analysis

Prior to analysis, descriptive statistics will be calculated to screen all variables for accuracy and to examine distributions.

All analyses will follow the intention-to-treat (“ITT”) principle, such that patients will be analyzed based on their assignment to the BH-VPN program or usual care. Balance in baseline characteristics between the groups will be assessed using Student’s t-test for normally distributed data, the Wilcoxon rank sum test for ordinal data or interval data that are not normally distributed, and the chi-square test for categorical data. Normality will be assessed using the Shapiro Wilk test and Q-Q plots.

The primary outcome, hospital admission (yes/no), is a binary dependent variable and will be compared between the BH-VPN and usual care groups using a generalized linear mixed-effects model with a logit link function. To adjust for correlation among patients seen on the same day and in the same ED, the model will include a random effect term for day nested within ED. The primary predictor in the model is an indicator for assignment to the BH-VPN program versus usual care. Additional baseline covariates will be included in the model if they are either strongly correlated with the dependent variable or show baseline imbalance between the two groups.

A similar approach will be used for the secondary outcomes to assess the patient-centric 45-day utilization rate, encounters with a self-harm diagnosis rate, and ED readmission rate. The models assessing these measures will be generalized linear mixed-effects models with a logit link, where utilization, diagnosis, or readmission, (yes/no) is the binary dependent variable. Independent variables in the models will be as described above for the primary analysis.

In addition, per-protocol analyses of the primary and secondary outcomes will be performed to evaluate the effect of BH-VPN program participation, in contrast to the ITT analysis evaluating the effectiveness of randomization to the program. The per-protocol analyses will include only subjects who received and adhered to the treatment (BH-VPN program or usual care).

Other binary outcome variables (e.g., frequency of patients active in the BH-VPN program) will be analyzed using descriptive statistics, unadjusted odds ratios, and 95% confidence intervals.

All tests will be two sided and the data will be analyzed using SAS Enterprise Guide 7.1 (SAS Institute Inc., Cary, NC, USA).

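### The per-protocol analysis of index admission selects program patients mainly from those already recommended for discharge, so it cannot estimate the effect of participation on that outcome

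*Combined protocol and SAP*

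**What the plan says.** Section 6.2 makes intention-to-treat by randomised day the main analysis. It then states that "per-protocol analyses of the primary and secondary outcomes will be performed to evaluate the effect of BH-VPN program participation", and describes the set in one sentence: "The per-protocol analyses will include only subjects who received and adhered to the treatment (BH-VPN program or usual care".

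The primary outcome (Section 5.1.1) is index admission: "This is a patient that presents to an Atrium Health ED and then is admitted for any reason".

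On who can take part, Section 5.3 says: "Patients that have a discharge recommendation on days the program is available, will be offered the BH-VPN program". The synopsis (Study Procedures) agrees. Enrolment is sought at that stage, and "Before discharge, the navigator will complete an initial virtual behavioral health assessment". The psychiatrist only recommends: "The ED physician will make the final decision on whether to admit or discharge the patient from the ED". The program's calls are timed from discharge (Section 5.4).

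Two places are looser. Section 3 says that patients with a consult on an intervention day "are provided the option of participating in the BH-VPN program", with no discharge condition. Section 5.3 also describes the navigator's approach after the recommendation as a repeat approach, which suggests some earlier contact.

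Section 5.5 lists completion for the intervention arm (for example "Enrolled for 45 days post ED admit date", or a move to another care management program). It also lists failure to complete: unreachable, died, or declined at the start or later. It does not mention the per-protocol set, and Section 6.2 does not mention Section 5.5. No section says what adhering to usual care means.

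**The concern.** For index admission, receiving the program comes after a step that largely decides the outcome. A patient usually becomes a participant because a psychiatrist has recommended discharge. Most of what would count as adherence is then observed after the ED disposition is known. Comparing such patients with all usual care patients, including those recommended for admission, produces a difference even if the program does nothing. Adjusting for baseline covariates does not repair this, because the selecting variable is a post-randomisation judgement about the outcome itself.

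The result would be labelled as the effect of participation and would stand beside the intention-to-treat result in the final report and manuscript foreseen in Section 10. A large and highly significant odds ratio there could be taken as support for the program when it shows only who was offered it.

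**Working it through.** **Inputs from the documents.** Usual care admission 60%, planned difference 8 points, target n = 1,133, design effect 1.1 (Section 6.1); equal numbers of program and usual care days (Section 5.2); two-sided tests (Section 6.2) at alpha 0.05 (Section 6.1). The plan gives no figure for the per-protocol analysis. I take n = 1,133 as given.

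**Assumed, because the documents are silent.**
- v: share of discharge recommendations that end in admission.
- u: uptake among those recommended for discharge.
- a: adherence among discharged patients.
- Every admission recommendation is followed.
- For set A, admitted and discharged patients participate and adhere equally often.

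**Yardstick.** Planned effect, 52% against 60%: OR = (0.52/0.48)/(0.60/0.40) = 1.083/1.5 = 0.72.

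**Set A (natural reading): participants against all usual care, no true effect.** Admission among participants is v, so OR = [v/(1−v)]/1.5.

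| v | OR |
|---|---|
| 5% | 0.0526/1.5 = 0.035 |
| 10% | 0.1111/1.5 = 0.074 |
| 20% | 0.25/1.5 = 0.17 |
| 40% | 0.6667/1.5 = 0.44 |
| 52% | 1.083/1.5 = 0.72 |
| 60% | 1.5/1.5 = 1 |

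The false odds ratio is more extreme than the whole planned effect at any share below 52%. It disappears only at 60%, where the recommendation carries no information.

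**False rejection for set A.** Usual care n = 1,133/2 = 566.5. The proportion recommended for discharge is d = 0.40/(1−v), so participants = 566.5 × d × u. Both group sizes are divided by 1.1, and a pooled two-proportion z-test stands in for the mixed model.
- v = 40%: d = 0.667. Participants are 566.5 × 0.667 × 0.25 = 94 at 25% uptake and 189 at 50%. The test rejects in 93.6% and 99.6% of trials.
- v = 50%: d = 0.80. Participants are 113 and 227. The test rejects in 47% and 69%.
- v = 20% or below: essentially always.

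**If contact sometimes comes earlier.** Let only a proportion s of the program set have a discharge recommendation, with the rest admitted. The set's admission rate is s·v + (1−s). At v = 10%:
- s = 0.9: 0.19, OR = (0.19/0.81)/1.5 = 0.16.
- s = 0.6: 0.46, OR = (0.46/0.54)/1.5 = 0.57.

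**Set B (less natural): keep admitted program-day patients, drop only discharged non-adherers.** With p the true program-day admission rate, OR = [p/((1−p)a)]/1.5.
- No effect (p = 0.60): 1.25 at a = 80% and 2.0 at a = 50%.
- Planned effect present (p = 0.52): 0.90 and 1.44.

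**Set C: limit both arms to patients recommended for discharge.** If the program acts only by changing the recommendation, v is the same in both restricted arms and OR = 1 whatever the true effect. An effect on the ED physician's final decision could remain, since the navigator's assessment precedes discharge. The comparison still conditions on a post-randomisation step that the program may change.

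**The case against.** The analysis is supplementary and set explicitly against intention-to-treat, and per-protocol comparisons are understood to be prone to selection. That limits the seriousness, but this is not the usual modest bias: receipt depends on a step close to the outcome.

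The intervention arm is not without definitions. Section 5.5 gives both completion and failure criteria, and an initial refusal can occur before discharge. This stands. A reader might infer that the sets are wholly undefined, or that adherence is always seen after the outcome is settled; the documents support neither. The gaps are the missing link from Section 5.5 to Section 6.2 and the absence of any definition for usual care.

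The exact sequence of contacts is also not certain, given Section 3 and the repeat approach in Section 5.3. The Appendix 1 diagram is not visible in the text available to me. So the program set is drawn mainly, not necessarily only, from discharge recommendations. The ED physician can also depart from the recommendation. The calculations allow for both, and the bias remains large over most of the range.

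The sizes rest on assumed shares, uptake and adherence, and on equal adherence in admitted and discharged patients. That last assumption fits poorly with calls timed from discharge. If admitted patients adhere less often, fewer of them remain in the set and the odds ratio moves further from 1.

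A reader might infer from set B that the plan would show harm. Set B fits poorly with an analysis of participation, because an admitted patient who was never offered the program did not take part. The synopsis does count every eligible program-day patient as exposed, but that describes assignment by day. Set B shows how far the result depends on set construction; it is not the likely outcome.

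**Conclusion.** The point holds for the per-protocol analysis of index admission. On the natural reading, and with no true effect, the odds ratio would be 0.035 to 0.44 if 5 to 40% of discharge recommendations end in admission, against a planned 0.72. Even at a 50% share, a 5% test would reject in roughly half to two-thirds of trials (47% and 69% at 25% and 50% uptake). These figures are conditional on the stated assumptions. The direction under the natural reading needs only that patients recommended for discharge are admitted less often than the 60% overall. None of the three constructions examined gives a valid estimate of the effect of participation on this outcome.

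A reader might infer that the trial's primary result is compromised. It is not: the intention-to-treat comparison by randomised day does not use participation or adherence. This should be fixed, but it concerns one supplementary analysis.

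**What to change.** In Section 6.2, delete the per-protocol analysis of index admission, so that intention-to-treat by randomised day is the only between-arm estimate for that outcome.

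If per-protocol analyses of the 45-day outcomes are kept:
- tie the intervention set to the completion and failure criteria in Section 5.5;
- restrict usual care to patients who were also recommended for discharge, or who were discharged;
- report the result as exploratory and non-randomised, stating that it conditions on a post-randomisation step the program may itself change, and on adherence measured within the outcome window.

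The restriction reduces the mismatch between arms but does not restore a randomised comparison, so the label is needed.

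The cost is SAP wording and the loss of one supplementary comparison. Sample size and primary analysis do not change. ED disposition is already tracked in the medical record (Section 5.1.1), so restricting usual care to discharged patients needs no new data.

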6.3. Data Collection Dates

The implementation of the BH-VPN will begin in October 2019 among patients with a completed telepsychiatric consult.

7. INTERVENTION PLAN

7.1. Navigator Assessments

The initial assessment within 72 hours will capture the following components:

- Communication method
- PHQ-9
- Insurance
- Primary care provider
- Outpatient Psychiatry provider
- Collateral resource
- Recent visit summary
- Substance abuse
- Medication barriers
- Appointment Barriers
- Transportation needs
- Access to medications
- Community Resources
- Columbia-Suicide Rating Scale to assess for suicide ideation

7.2. Follow-up Assessments

The weekly follow-up contact assessments may be comprised of the following components:

- Columbia-Suicide Rating Scale to assess for suicide ideation
- PHQ-9
- Appointment reminder\follow-up
- Medication access barriers
- Substance use disorder follow-up
- Supportive listening

- Psychoeducation
- Utilization of community resources
- Crisis planning and adherence to the plan by the patient

8.1. Protocol and Pathway Training

Background, protocol and process steps will be presented to psychiatrists and nurse practitioners who will be providing virtual psychiatric consultations. The role of virtual patient navigator and randomization scheme will be presented so expectations are clear that this is not available every day/time or weekends. This will be presented at the Department of Psychiatry meeting, which includes Emergency and Telepsychiatry Departments. Attendees may also include providers, who at some point may see patients who have been through this pathway but will not be directly involved in providing evaluations. Education will be provided to the emergency department staff involved in this project, so that they are aware of the process and the role of the virtual patient navigator.

9. SAFETY RISKS AND REPORTING

The data collection and intervention for this project presents no more than minimal risk to patients. The implementation of the BH-VPN program and its components complement ongoing patient care through virtual patient navigation within Atrium Health. The BH-VPN program is currently offered at 10 urban EDs within Atrium Health. This study is evaluating the BH-VPN program among additional rural EDs that will offer the program to their patients. The addition of an evaluation design that aligns with existing patient care where there are limited resources thus confers minimal additional risk to patients.

Other potential risks of participation in this project include, the risk of health information disclosure. There is always the risk of disclosure of a patient's private health information (PHI) or medical information. However, the processes identified in this protocol to enable the execution of this project, do not increase inherent risk of disclosure. Atrium Health utilizes several hard and soft safety controls in the protection of patient information and medical records. Security controls include, but are not limited to, multiple system firewalls, access restrictions to patient records and information, locked offices and buildings housing research and patient data, and multiple layers of username and password protected computer and system access. The project team will ensure that appropriate handling of patient PHI follows standard Atrium Health procedure. In the event of PHI disclosure, the appropriate internal departments will be informed and processed per legislation and privacy regulations.

9.1. Data Quality Assurance

This study will be organized, performed, and reported in compliance with the study protocol, standard operating procedures (SOPs) of CORE and Atrium Health, and other applicable regulations and guidelines (e.g. GCP).

9.2. Data Monitoring by the Sponsor

The conduct of this project will abide by standard operating procedures set forth by both Atrium Health and CORE. The Principal Investigators, statistician, and other team members will meet as needed to review enrollment and retention, study progress, and validity/integrity of the data. Documentation of these meetings will be kept with study records.

10. RESEARCH COMPLETION

The Principal Investigator has the right to close the project at any site any time.

For any closure, the following applies:

- Closures should occur only after consultation between involved parties.
- In case of a partial study or site closure, patients still participating in the BH-VPN program, or those who are considered in follow-up, must be taken care of in an ethical manner.

The study will be considered complete when one or more of the following conditions is met:

- The enrollment period has ended, and the data collection period is complete.
- All subjects have dropped out or discontinued from the study after the enrollment period is completed, but prior to data collection cutoff.
- The IRB or Principal Investigator discontinues the study.
- The Principal Investigator defines an administrative or clinical cut-off date.

Upon study completion, a final report will be presented to the Executive Committee and all key stakeholders. The final report will detail findings including primary, secondary and exploratory outcomes. The team will also prepare a manuscript for publication focused on outcomes and feasibility of implementation of the BH-VPN program.

11. ETHICAL AND LEGAL ISSUES

11.1. Ethical and Legal Conduct of the Study

The procedures set out in this protocol, pertaining to the conduct, evaluation, and documentation of this study, are designed to ensure that the Investigators abide by Good Clinical Practice (GCP) guidelines and under the guiding principles detailed in the Declaration of Helsinki. The study will also be carried out in keeping with the applicable local laws and regulation(s).

Documented approval from appropriate agencies (e.g. IRB) will be obtained before the start of the study, per GCP, local laws, regulations, and organizations.

Strict adherence to all specifications laid down in this protocol is required for all aspects of study conduct.

Modifications to the study protocol will not be implemented without consulting the Principal Investigator and IRB approval, as applicable. The Principal Investigator must assure that all study personnel, including co-investigators and other study staff members, adhere to the study protocol and all applicable regulations and guidelines regarding research both during and after study completion.

The Principal Investigator will be responsible for assuring that required data will be collected and properly documented.

